# f. Methods for providing anonymity or confidentiality. For research involving patients, describe how HIPAA requirements will be met.

Each subject will create his/her own identifying code based on personal information. The identifier will be created using the following criteria:

- The 3 first letters of the month (in English) of your MOTHER'S birthday (e.g., SEP)
- YOUR 2-digit birthday date (e.g., Ø8 for May, 8th) (01-31)
- The first letter of YOUR MIDDLE NAME; enter X if you do not know or have a middle name (e.g. M for Mary) (A-Z)
- The total number of OLDER SIBLINGS you have, including living, deceased, and half (e.g., 0 if you are an only child; enter 9 if you have 10 or more siblings) (0-9)

For the examples given above, the identifier would be SEP08M0 (SEPØ8MØ). Identifiers using these variables have been shown to be highly repeatable, and there are processes for linking identifiers that are mismatched by one element. (Yurek, 2008) Once data collection is complete, all subject email addresses will be deleted from the research data. The email address will be retained by [name] as long as these individuals choose to use the on-line Pilates program, in the same way that typical customer information is retained. Research subjects may request that their emails be deleted by [name] if they no longer want to access the Pilates modules.

g. Plan for destroying private, identifiable data at the end of the research project. (You must request approval for continuation annually until all private, identifiable data has been destroyed.) Subjects' email address is the only identifying information that is collected during this research. Once a subject has completed the study, that person's email address will be deleted from the research data. Identifying codes will be discarded after all data for a given individual have been collected and entered into the computer of the primary researcher, [name].

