sessions and, if so, why. We will also ask if they have any comments about the modules or about their experience. We will also ask about any changes in pain, either related to the Pilates practice, or unrelated. The contact email will also remind them that they can contact one of the PI (JD) if they have questions or problems with the Pilates, or (LR) if they have any questions about research participation.

At the end of 8 weeks, subjects will be asked to repeat the initial questionnaires on SurveyMonkey, and comment on their experience doing the Pilates. This is likely to take about 60 minutes. Subjects will continue to have access to the Pilates modules and we will encourage them to continue using the modules. We will track whether individuals do access the modules over the next 6 months.

Six months after subjects complete the 8 week exercise session, we will contact each subject again and ask him/her to repeat the initial questionnaires on SurveyMonkey, and again comment on whether they felt the Pilates was helpful.

We will also include an 8-week wait-list group constructed from subjects asking to participate after we have already recruited 225 subjects. This wait list is primarily because we do not want to be so overwhelmed by participants that we cannot manage them effectively (responding to questions about the Pilates, sending out follow-up surveys, etc.). Also, a wait-list group would provide a control group (albeit not randomly selected). All participants who do not start in the initial group will be asked if they still want to participate in a wait-list group; if they do, we will contact them 8 weeks after their initial surveys were completed, ask them to repeat the surveys, then start them in the Pilates program.

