There is minimal risk of private information being revealed, as subjects will use an ID code known only to them for their data on SurveyMonkey. Thus, all of the survey data will be collected, stored and analyzed without any personal identifiers. Access to the Pilates course will be tracked using subjects' email address and their self-generated research code; only [name] will know subjects' email address, but she will not have access to personal information shared on SurveyMonkey. Reminder emails will be sent out by [name] using subjects' email address, but these emails will link to SurveyMonkey where subjects can enter their self-generated research ID. Subjects will not email any information to [name] as part of the research (though they are allowed to contact her independently with questions about the exercises, as are all users of her programs). [name] and [name] will have access to the SurveyMonkey data, but will not have email addresses. Since subjects will receive access to the Pilates course free of charge, subjects will not be providing credit card information.

We will be asking for qualitative information in the weekly check-in. Although we will explicitly ask subjects to not include any identifiable information in these narrative responses, it is possible that they might. Any identifiable information will be deleted when narrative data are extracted from SurveyMonkey for further data analysis.

b. For subjects in the EU, Iceland, Liechtenstein, and/or Norway, describe how you will comply with GDPR regulations. For additional information about the GDPR, please see https://rgs.usu.edu/irb/wp-content/uploads/sites/12/2018/04/GDPR-Guidance.pdf. According to GDPR regulations, we will be collecting Personal Data as we will be using subjects' email address to contact them, send them links to surveys, and enroll them in the Pilates course. All data entered into SurveyMonkey (all data except utilization of the on-line modules) will be through a subject-generated identification code, so the data in SurveyMonkey will be anonymous. [name], who runs the on-line Pilates courses, will have email addresses and the subject-generated ID

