code so that we can track compliance, but she will not have direct access to the remaining data. All data will be stored using the subject-generated ID code. Once data collection for any individual is complete, that person's email address will be deleted from the research data, which will then be anonymous. [name] will continue to have access to the email address as long as that individual wants to continue accessing the Pilates modules.

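### Survey waves are joined only by a self-made code that subjects re-enter each time; one-element repair is invoked without a matching order, tie rule or assured second key, and cheap data-collection changes would protect the linkage

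*Combined protocol and SAP*

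**What the plan says.** Section 7f builds the code from four facts: mother's birth month, the subject's own day of birth, middle initial (X if there is none) and number of older siblings. It calls such codes highly repeatable and adds that "there are processes for linking identifiers that are mismatched by one element", with a citation. It does not say which process will be used, which records are candidates, in what order matches are made, or what happens to ties. The analysis section (6e) does not mention linkage.

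Section 7b states: "All data will be stored using the subject-generated ID code". Under section 7a, the researchers who see the survey data have no email addresses. Module use is handled differently: "Access to the Pilates course will be tracked using subjects' email address and their self-generated research code". The instructor who holds that list cannot see survey answers.

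Subjects enter the four elements at baseline (Appendix C), in each weekly survey (Appendix H) and in the 8-week and 6-month surveys (Appendix I.2). Appendix C asks age and gender; Appendices H and I.2 do not. Section 6a says the initial questionnaires are repeated at follow-up, without saying whether that includes the demographic form.

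On retention, section 7g says: "Identifying codes will be discarded after all data for a given individual have been collected" and entered into the primary researcher's computer.

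**The concern.** All the quantitative analyses of change in section 6e need each follow-up record attached to the right baseline record: the repeated-measures ANOVA, the comparison of 8-week change between the Pilates and wait-list groups, and the regressions that include compliance. Each subject re-enters the code about ten times (eight weekly surveys, the 8-week survey and the 6-month survey), and wait-list subjects once more after their waiting period. Some entries will contain an error.

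Repairing an error means looking for a baseline code that differs in one element. If the code space is small relative to the sample, a different person may fit as well as the right one. Two people may also share a code exactly, and one-element repair cannot resolve that. A false link replaces a within-person change with a difference between two people. Leaving ambiguous records out loses data that could have been kept. Once codes have been destroyed, a doubtful link cannot be audited or undone.

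**Working it through.** The documents state no duplicate, mismatch or ambiguity rate, so there is no figure to reproduce.

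**Inputs from the plan.** Code elements have 12, 31, 26 and 10 levels (section 7f). The planned number is 500 (section 4a). The wait list forms "after we have already recruited 225 subjects" (section 6a), and section 4e makes it equal in size, which implies about 450.

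**Code space.** 12 × 31 × 26 × 10 = 96,720. Codes differing from a given code in exactly one element: 11 + 30 + 25 + 9 = 75, or 76 counting the code itself.

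**Exact duplicates, uniform codes, N = 500.** Pairs of subjects: 500 × 499 / 2 = 124,750. Expected duplicate pairs: 124,750 / 96,720 = 1.29. Chance of at least one: about 1 − exp(−1.29) = 72.5% (exact product 72.5%, reported as 73%). Expected pairs one element apart: 124,750 × 75 / 96,720 = 97.

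**Ambiguous repairs, uniform codes, all other baseline records as candidates.** P(at least one false candidate) = 1 − (1 − 76/96,720)^(N − 1):
- N = 500: 32.4% (simulation 32.7%)
- N = 450: 29.7%
- one group of 225: 16.1%

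Reaching one third under uniformity needs ln(2/3) / ln(1 − 76/96,720) = 516 other records.

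**Skewed codes (assumed).** The code cannot be uniform: everyone without a middle name enters X, and low sibling counts will dominate. Assumed percentages for 0 to 9 older siblings:
- mild skew: 35, 25, 15, 9, 6, 4, 2.5, 1.5, 1, 1
- strong skew: 42, 31, 14, 6.5, 3, 1.5, 1, 0.5, 0.3, 0.2

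Mild skew also uses unequal initials (relative weights A to Z: 10, 3, 5, 4, 7, 2, 3, 3, 2, 9, 4, 8, 9, 3, 1, 3, 0.3, 8, 6, 3, 0.3, 2, 2, 5, 1, 0.5). Strong skew scales these to 80% and puts a further 20% on X. Both give days 29 to 31 lower weight. A third case uses only the strong sibling skew.

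Expected duplicate pairs are 124,750 times the product of the four sums of squared frequencies:
- mild: 124,750 × 0.0833 × 0.0324 × 0.0581 × 0.2218 = 4.3
- strong: 124,750 × 0.0833 × 0.0324 × 0.0925 × 0.2976 = 9.3
- siblings only: 124,750 × 0.0833 × 0.0323 × 0.0385 × 0.2976 = 3.8

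Simulated share of repairs with a false candidate, all baseline records open:

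| N | Uniform | Skewed |
|---|---|---|
| 500 | 33% | 58–69% |
| 450 | 28% | 55–66% |
| 225 | 16% | 35–47% |

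**Exact matches set aside first, N = 500.** Only baseline records not yet matched remain as candidates. Ranges cover assumed error rates of 5–20%:

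| Attrition (assumed) | Uniform | Skewed |
|---|---|---|
| 0% | 3.1–7.5% | 5.2–28.5% |
| 20% | 8.0–13.2% | 20–43% |
| 40% | 16.4–18.5% | 34–51% |
| 60% | 21.6–23.8% | 45–59% |

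Attrition matters because the baseline records of people who have left stay in the pool as false candidates.

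**People affected.** If all 500 responded and 5–20% made a one-element error (assumed), there would be 25 to 100 repairs at a wave. Ambiguous repairs would number from 25 × 0.031 = 0.8 to 100 × 0.687 = 69. In the uniform, all-records case they run from 25 × 0.324 = 8 to 100 × 0.324 = 32.

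**Effect of one false link.** With equal variances and test-retest correlation r, a true change has variance 2σ²(1 − r). A difference between two unrelated people has variance 2σ². The ratio is 1/(1 − r): 2 at r = 0.5 and 5 at r = 0.8 (assumed values).

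**The case against.** - **Size.** A reader might infer that at least a third of repaired links would be ambiguous. The documents do not support this as a lower bound: uniform codes against all 500 records give 32%, and setting exact matches aside first, as standard linkage does, can bring the share to a few per cent. An ambiguous repair is also not a wrong link; it only has more than one candidate.
- **Second key.** A reader might infer that none exists. Module-use records carry email plus registered code, so they do not depend on a re-entered code. Age and gender would be available on the surveys if section 6a means the demographic form to be repeated. What stands is that neither follow-up form shows a tie-break field and that email cannot be joined to the surveys as planned.
- **Error rate.** Every form prompts for the same fixed personal facts, and section 7f cites evidence of repeatability. Errors may be rare. The plan gives no rate, and exact duplicates arise even with no errors.
- **Reliance on repair.** Section 7f says that processes exist; it does not commit to accepting every near match. The cited process may require uniqueness, but the plan does not say so.
- **Bias.** A reader might infer that mean change is biased. Random false links within a group mainly add noise and do not by themselves shift the group mean. Links that cross groups would dilute the group contrast.
- **Discarding codes.** Removing people whose data are complete also removes false candidates for later repairs. The remaining harm is that earlier links can no longer be audited or reversed.
- **Pilot status.** Section 3 calls this a pilot, so a missing tie rule alone would be a documentation gap. The fields and emails that prevent the problem, however, cannot be added after data collection.

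**Conclusion.** The point holds as a cheap improvement. Survey waves are linked by one re-entered code, one-element repair is mentioned without a rule, a second key on the follow-up surveys is not assured, and codes are discarded person by person.

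The firmest figures assume uniform codes and 500 subjects: about 1.3 duplicate pairs, a 73% chance of at least one, and a false candidate for about 32% of repairs against all baseline records. The wider range of 3% to 69% rests on assumed skew, attrition, error rate and candidate pool. Much of its width comes from choices that the plan leaves open. The likely consequences are noisier change scores, weaker compliance associations and avoidable loss of records. A systematic shift in mean change has not been shown.

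**What to change.** 1. Have the sender of the reminder emails, who already holds email and code, merge each subject's registered code into the weekly, 8-week and 6-month emails, and into the wait-list group's repeat-survey request.
2. Check for exact duplicates at enrolment and give the second holder a suffix.
3. Add a tie-break field at baseline and on every follow-up survey, such as year of birth, or age allowing a one-year rise by the 6-month survey. Gender will separate few people, since section 4a expects a mostly female sample. If birth years were spread evenly over the 53 eligible ages (18 to 70), the 32.4% would fall to 1 − (1 − 76/(96,720 × 53))^499 = 0.7%; with half as many effective years, about 1.5%.
4. State the rule in section 6e: match exactly first, accept a one-element repair only when it is unique and the tie-break field agrees, and otherwise leave the record unlinked.
5. Report linked, repaired, ambiguous and unlinked counts by wave and group.
6. Keep codes until linkage is complete for the whole study, and amend section 7g accordingly.

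The cost is a mail-merge field, one question per survey and a short paragraph. Codes are kept longer and one more quasi-identifier is collected, so the confidentiality terms need updating. Section 7a and Appendix C describe the code as known to the subject alone, while sections 7a and 7b have the instructor holding it with the email address. Those statements need reconciling whether or not the code is put in the emails.

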### h. Benefits to participants:

Subjects will be able to participate in on-line Pilates training free of charge, and will be allowed to continue using the on-line training after the research is completed.

### i. Benefits to society from the research:

Very little is currently known about efficacious treatments for HSD/EDS, so this pilot study will help direct ongoing research. Also, this research establishes a format for pilot data collection for on-line training that is potentially feasible for additional interventions; this would facilitate more clinical research regarding treatments for HSD/EDS in the future. If, as anecdotal evidence suggests, Pilates is beneficial for people with HSD/EDS, this research may benefit this population by increasing awareness of this treatment approach.

psychosocial, or contribute to the participation in re	vel. A research benefit is considered to be something of health-related, other value to an individual research subject, or something that will acquisition of generalizable knowledge. Money or other compensation for esearch is not considered to be a benefit, but rather compensation for inconveniences. Check the most appropriate benefit level, below:
population  No prospec  may benefit	ct of direct benefit to individual subjects, but likely to yield generalizable knowledge about group to which the subject belongs; ct of direct benefit to individual subjects, but likely to yield generalizable knowledge that it a population group to which the subject belongs; or ch involves the prospect of direct benefit to participating subjects.
been FDA approved	vice Exemption (IDE): Does this research involve any device that has not or which is being used for a purpose for which it has not been approved? If arkson's guidelines regarding IDE. What are the results of safety testing

# 9. Conflict of interest statement:

performed for this device?

One of the researchers (JD) has a financial interest in the Pilates training program being offered. While her role is essential for the intervention and data collection, data analysis will be performed by the other researchers who have no financial interest.

### **Appendix C: Initial Demographic and Health History**

research identification code that only you will know, but that you can recreate for participation in future components of this study. \_\_\_\_ The 3 first letters of the month (in English) of your MOTHER'S birthday (e.g., SEP) YOUR 2-digit birthday date (e.g., Ø8 for May, 8th) The first letter of YOUR MIDDLE NAME; enter X if you do not know or have a middle name (e.g. M for Mary) The total number of OLDER SIBLINGS you have, including living, deceased, and half (e.g., 0 if you are an only child; enter 9 if you have 10 or more siblings) • In this example, your identification code would be SEP08M0 (SEPØ8MØ) • Your 7-character research code is: (provided by the computer) 5. Age: 6. Gender □Female □Male □I define myself as other than Female/Male 7. How many years ago were you diagnosed with HSD/EDS? \_\_\_\_\_\_ 8. When did you begin to have symptoms from HSD/EDS? \_\_\_\_\_ 9. Work status (check all that apply): □Full time □Part time □On disability □Retired □Unemployed □Student □Home-maker 10. Comorbidities (check all that apply): **Current** Past □ □ Allergies □ □ Anxiety ☐ ☐ Asthma ☐ Chronic Fatigue Syndrome/Myalgic Encephalitis (CFS/ME) ☐ ☐ Degenerative spinal condition (neck, mid, or low back) □ □ Depression □ □ Diabetes ☐ Endometriosis, polycystic ovary syndrome or other gynecological condition ☐ ☐ Fibromyalgia ☐ ☐ Gastro-Esophageal Reflux Disorder (GERD) ☐ ☐ Gastroparesis or dysmotility ☐ ☐ Hypo/hyperthyroidism ☐ ☐ Irritable Bowel Syndrome (IBS) ☐ ☐ Mast Cell Activation Syndrome/Disorder (MCAS/D) □ □ Osteoarthritis ☐ Postural Orthostatic Tachycardia Syndrome (POTS) or orthostatic hypotension ☐ ☐ Raynaud's □ Rheumatoid arthritis □ □ Sleep disorder

To help keep your data confidential while still being able to track changes over time, we would like you to create a

CU IRB Protocol Form 21 Last Revised 2018.07.12

Other conditions, not listed above: \_\_\_\_

☐ I have other conditions I choose not to list here

	TT.		5	-ite	m Questionnaire for historical hypermobility
		Y	/	N	Can you now (or could you ever) place your hands flat on the floor without bending your knees?
		Υ	/	Ν	Can you now (or could you ever) bend your thumb to touch your forearm?
		Y	/	N	As a child, did you amuse your friends by contorting your body into strange shapes or could you do the splits?
		Y	/	N	As a child or teenager, did your shoulder or kneecap dislocate on more than one occasion?
		Y	/	N	Do you consider yourself "double-jointed"?
				a.	If Yes, how many months ago did you last get treated in PT: months by you currently do regular exercise? If so, please check the amount
		<1	15	min	most days, $\square$ 15-30 min most days, $\square$ >30 min most days
14.	Y	/	N	На	ave you participated in any Pilates in the past? If Yes: how much time/week do you spend
	dc	oin	g F	Pilat	es exercises (enter 0 if none):
15.	Υ	/	N	Ha	ave you participated in any type of mind-body training (other than Pilates) in the past?
	Th	iis	w	ould	include Feldenkrais, Tai Chi, qigung, Yoga, etc. If Yes: what type:

This form will be entered into SurveyMonkey, so formatting will change, slightly, and subjects will not be asked to compute scores.

# BRISTOL IMPACT OF HYPERMOBILITY (BIOH) QUESTIONNAIRE

This questionnaire is designed to ask how hypermobility affects your day to day life. Please answer all of the questions and try not to think too much about your answer.

A.	During the pas	t 7 day	/s , ha	ve you	ı had	pain i	n any	of the	e follo	wing a	reas?
						Υe	es				No
Shou	ılders										
Elbo	ws										
Wris	ts										
Hand	ds										
Hips											
Knee	es										
Ankl	es										
Feet											
Neck	(										
Back											
В.	We would like to the past 7 days Please circle th	i .						nced	pain a	ind fat	igue due to hypermobility during
1)	your average le	vel of p	ain di	uring t	he pa	ast 7 d	lays				
	0 No pain	1	2	3	4	5	6	7	8	9	10 Worst imaginable pain
2)	your worst level	of pair	n durii	ng the	past	7 day	'S				
	0 No pain	1	2	3	4	5	6	7	8	9	10 Worst imaginable pain
3)	how much pain	you ha	ve had	d whe	n wal	lking	during	the I	past 7	days	
,	0 No pain	1	2	3	4	5	6	7	8	9	10 Worst imaginable pain
4)	how much pain	you ha	ve ha	d whe	n res	ting d	uring	the p	ast 7	days	-
	0 No pain	1	2	3	4	5	6	7	8	9	10 Worst imaginable pain
5)	your average le	vel of fa	atigue	durin	g the	past 7	7 day	s			· ·
,	0 No fatigue	1	2	3	4	5	6	7	8	9	10 Totally exhausted
6)	the effect fatigue	e has h	nad or	ı your	life di	uring t	he pa	st 7	days		•
,	0 No effect	1	2	3	4	5	6	7	8	9	10 Large effect
7)	how well you ha	ve co p	ed wi	th fation	gue d	uring t	he pa	ast 7	davs		*Reverse scored (0=10, 1=9, etc)
,	0 Not at all well	1	2	3	4	5	6	7	8	9	10 Very well
											/70

Page 1 of 4

© University of the West of England, Bristol (2013)

C.	Please tick the box which best describes how much, during the past 7 days, hypermobility has affected								
		Not at a	II  A little 	Somewhat 	A lot 	Completely 			
8)	the footwear you have worn								
9)	the transport you have used								
D.	How often	Never  (	0	Sometimes 	Often 	Al			
10)		Never (	Occasionally 	Sometimes	Otten	Always⁵			
10)	have you had unexpected pain (that was not an expected consequence of something you have done) during the past 7 days?								
11)	has your wrist or hand given way, leading you to drop, or nearly drop something during the past 7 days?								
12)	has your ankle, knee or hip given way, leading to a stumble or trip during the past 7 days?								
13)	have you lost your balance during the past 7 days?								
14)	have joints seized up during the past 7 days?								
15)	has it felt like a joint has slipped out of place during the past 7 days?								
16)	have you had muscle cramps or spasms during the past 7 days?								
17)	has your sleep been disturbed due to pain or discomfort during the past 7 days?								
						/50			
Ε.	How much difficulty have you hypermobility?	u had with t	he following tas	ks during the pas	st 7 days due				
		Not difficu			Extremely difficult 	Completely impossible 			
18)	Bending or twisting								
19)	Squatting								
20)	Walking on uneven ground								
21)	Carrying a heavy bag, such as a shopping bag								
22)	Reaching up to high shelves								
23)	Pulling or pushing heavy doors								
24)	Opening a tight or new jar								
Page	2 of 4		c	University of the \	West of Englan	d, Bristol (2013)			

CU IRB Protocol Form 24 Last Revised 2018.07.12

		di	Not ifficult 	A little difficult	Somewh difficult		Completely impossible 
25)	Writing for more than 30 minutes						
26)	Peeling or chopping vegetables						
27)	Carrying a saucepan full o water	of					/50
F.	How much discomfort w	ould you h	ave had at	ter the follo	owing activitie	s during the pa	
	dis	No comfort 		ghtly fortable 	Uncomforta	ble  Painful 	Could not do it 
28)	Standing up for more than 30 minutes		I				
29)	Sitting in a chair for more than 30 minutes		ı				
30)	Standing up after sitting for more than 30 minutes		ı				
31)	Climbing several flights of stairs		1				
32)	Going down several flights of stairs		I				
33)	Walking at your own pace for a few miles		I				
34)	Walking briskly for a few miles		I				
35)	Wandering around shops or museums		1				
36)	Bending or twisting						
37)	Squatting		I				
							/50
G.	Please circle the numb	er which be	est indicate	es			
38)	how much you have felt in			-	•		ast 7 days
	0 Completely in control	1 2	3 4	5 6	7 8	9 10 Completely una	ble to control
39)	how accurately you have I	been able t	o predict h	now you mi	ght feel in ger		
,	0	1 2	-	5 6	7 8	9 10	-
	Always able to predict					Completely una	ble to predict
40)	how frustrated you have for	elt with hyp 12	ermobility 3 4	during the	past / days 7 8	9 10	
	Not at all frustrated				, ,	Very frust	rated
41)	how strong your body and	limbs have	e felt gene	rally over t	he past 7 day	'5	
	Vonustrana	1 2	3 4	5 6	7 8	9 10 Extremely	work
	Very strong					Extremely	WEDK

Page 3 of 4 © University of the West of England, Bristol (2013)

	how 'tight', 'strong',		_	_	body an			_		_		it r uays
	Very tig	0 1	2	3	4	5	6	7	8	9	10 Extremely lo	voca.
43)	how able you have t		ontrol v	our fa	tique in	the n	ast 7	davs			Extremely it	use
,	non able you have	0 1	2	3	4	5	6		8	9	10	
	Completely in contro	ol									No control w	hatsoever
44)	how much you have				ır pain ir		past 7	day			40	
	Completely in contro	0 1 ol	2	3	4	5	0	-	8	9	10 No control w	hatsnever
45)	how much you have		control	of you	ır life in	the pa	ast 7	days			110 0011110111	illusoc vei
	•	0 1	2	3	4	5	6	7	8	9	10	
	Completely in contro	ol									No control w	hatsoever
H. activ	Thinking about whities during the past			ually a	ble to d	o, hov	v muc	h has	hype	mobil	ity interfered	with your
	Please circle the	number	r which	best :	shows.							
46)	how much hypermo	_				_			_	_	_	
	Not at	0 1 all	2	3	4	5	6	7	8	9	10 Unable to de	0
47)	how much difficulty	you hav	e had	in carr	rying ou	t your	desir	ed le	vel of	exerci	se during the	past 7 days
		0 1	2	3	4	5	6	7	8	9	10	
	No difficul	lty									Extreme dif	ficulty
												/100
I.	Please tick the bo	x which	best d	escrib	es your	agree	ement	with	the fo	llowing	g statements	
I.	Please tick the bo	x which	best d						Nei	ther		
I.	Please tick the bo	x which	best d		es your Strongl agree	y	Agre		Nei agr		g statements Disagree	Strongly disagree
I. 48)	Please tick the bo				Strong	y		ee	Nei agr disa	ither ee or		Strongly
		feel stro	ong		Strongl agree	y	Agre	ee	Nei agr disa	ither ee or agree	Disagree	Strongly disagree
48)	My body does not	feel stro	ong conditi	ion	Strongl agree	y	Agre	ee	Nei agn disa	ither ee or egree 3 3	Disagree	Strongly disagree
48) 49) 50) 51)	My body does not: I am concerned ab getting worse I feel frustrated wit My coordination is	feel stro out my h my co poor	ong conditi ondition	ion	Strongl agree	y	Agre	ee	Nei agn disa	ither ee or egree	Disagree	Strongly disagree
48) 49) 50)	My body does not: I am concerned ab getting worse I feel frustrated wit My coordination is I feel that I could to time	feel stro out my h my co poor rip or fal	ong conditi ondition	ion 1	Strongl agree	y	Agre	ee	Nei agridisa C	ither ee or egree 3 3	Disagree	Strongly disagree
48) 49) 50) 51)	My body does not I am concerned ab getting worse I feel frustrated wit My coordination is I feel that I could tr	feel stro out my h my co poor rip or fal	ong conditi ondition	ion 1	Strongl agree	y	Agre	ee	Nei agn disa C C	ither ee or agree ]  ]  ] 	Disagree	Strongly disagree
48) 49) 50) 51) 52)	My body does not I am concerned ab getting worse I feel frustrated wit My coordination is I feel that I could tr time I can control the m	feel stro out my h my co poor rip or fal ovemer	ong condition andition I at any	ion 1	Strongl agree	y	Agree	ee i	Nei agn disa C C C	ither ee or ogree 3' 3' 3' 3' 3'	Disagree	Strongly disagree
48) 49) 50) 51) 52)	My body does not: I am concerned ab getting worse I feel frustrated wit My coordination is I feel that I could tr time I can control the m limbs I feel that I can ren	feel stro out my th my co poor ip or fal ovemer	ong condition andition I at any ont of my	ion 1	Stronglagree	y	Agre	ee	Nei agn disa C C C	ither ee or agree	Disagree	Strongly disagree
48) 49) 50) 51) 52) 53)	My body does not I am concerned ab getting worse I feel frustrated wit My coordination is I feel that I could tr time I can control the m limbs I feel that I can renactive I feel that I can ma	feel stro out my th my co poor ip or fal ovemer	ong condition andition I at any ont of my	ion 1	Stronglagree	y	Agre	ee	Nei agn disa C C C	ither ee or agree	Disagree	Strongly disagree
48) 49) 50) 51) 52) 53)	My body does not: I am concerned ab getting worse I feel frustrated wit My coordination is I feel that I could tr time I can control the m limbs I feel that I can ren active I feel that I can ma condition	feel stro out my th my co poor rip or fal overner nain phy	ong condition andition I at any out of my ysically	ion n y y	Stronglagree	ly .	Agree d'all	2	Nei agn disa C C C C	ither ee or agree	Disagree	Strongly disagree

CU IRB Protocol Form 26 Last Revised 2018.07.12

